3.6.1.3 Cetuximab exposure

The dose information will be assessed by the following:

- Total number of cycles started for cetuximab per participant
- Duration of cetuximab (in months) is defined by (date of last administration of cetuximab + 7 – date of first administration of cetuximab)/30.4375.
- Actual dose (mg/m²)
- Cumulative dose (mg/m²): the cumulative dose is the sum of all actual doses of cetuximab, given from first to last administration
- Actual dose intensity (ADI in mg/m²/week): defined as the cumulative dose divided by the duration of cetuximab exposure (in weeks)
- Planned dose intensity (PDI in mg/m²/week): corresponds to the sum of planned dose started and divided by duration of cetuximab exposure (in weeks)
- Relative dose intensity (RDI, in %): $100 \times \frac{\text{ADI (mg/m}^2\text{/week)}}{\text{PDI (mg/m}^2\text{/week)}}$

The total number of cycles started; number of cycles started by participant will be summarized by category. Duration of cetuximab exposure, cumulative dose, ADI and RDI will be summarized quantitatively. Relative dose intensity will also be summarized by category if relevant.

The following variables will be derived to describe dose modifications and dose interruptions:

- Dose reduction: The first and second administration will not be counted as a dose reduction. For the third and subsequent cetuximab administrations, dose reduction will be determined using the dose level intervals provided in [Table 5](#), by comparing the current dose level to the previous dose level. If the current dose level is below the dose level interval of the previous dose administration, then the current dose level is considered reduced.

Table 6 - Cetuximab dose reduction criteria

Actual dose level	Dose level interval
150 mg/m ²	>0 and ≤175 mg/m ²
200 mg/m ²	>175 mg/m ² and ≤225 mg/m ²
400 mg/m ² then 250 mg/m ²	>225 mg/m ²

- Dose omission is defined as a dose not administered at the scheduled visit.
- Dose interruption: A dose will be considered as interrupted if cetuximab administration is stopped during an infusion regardless of whether it is restarted or not.

Dose modifications and dose interruptions will be analyzed by participant as follows:

- **Participant** (number of participants treated will be used as denominator)
 - Number (%) of participants with at least 1 dose modification
 - Number (%) of participants with at least 1 dose reduction
 - Number (%) of participants with at least 1 dose omission
 - Number (%) of participants with at least 1 dose interruption
 - Number (%) of participants with at least 1 dose interrupted and restarted
 - Number (%) of participants with at least 1 dose interrupted and not restarted
 - Number (%) of participants with at least 2 dose interruptions.

3.6.1.4 *Pembrolizumab exposure*

The dose information will be assessed by the following:

- Total number of cycles started for pembrolizumab per participant
- Duration of pembrolizumab (in months) is defined by (date of last administration of cetuximab + 21 – date of first administration of pembrolizumab)/30.4375.
- Actual dose (mg)
- Cumulative dose (mg): the cumulative dose is the sum of all actual doses of pembrolizumab, given from first to last administration
- Actual dose intensity (ADI in mg/week): defined as the cumulative dose divided by the duration of pembrolizumab exposure (in weeks)
- Planned dose intensity (PDI in mg/week): corresponds to the planned dose at C1D1 divided by the theoretical cycle duration expressed in weeks (ie, 3 weeks)
- Relative dose intensity (RDI, in %): $100 \times \frac{\text{ADI (mg/week)}}{\text{PDI (mg/week)}}$

The total number of cycles started; number of cycles started by participant will be summarized by category. Duration of pembrolizumab exposure, cumulative dose, ADI and RDI will be summarized quantitatively. RDI will also be summarized by category.

The following variables will be derived to describe dose modification and dose interruptions:

- Dose omission is defined as a dose not administered at the scheduled visit.
- Dose interruption: A dose will be considered as interrupted if pembrolizumab administration is stopped during an infusion regardless of whether it is restarted or not.

Dose modifications and dose interruptions will be analyzed by participant as follows:

- **Participant** (number of participants treated will be used as denominator)
 - Number (%) of participants with at least 1 dose omission
 - Number (%) of participants with a least 1 dose interruption
 - Number (%) of participants with at least 1 dose interrupted and restarted
 - Number (%) of participants with at least 1 dose interrupted and not restarted
 - Number (%) of participants with at least 2 dose interruptions.

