1.1 STUDY DESIGN

This is a Phase 2, multi-cohort, un-controlled, non-randomized, open-label, multi-center study assessing the antitumor activity and safety of SAR444245 combined with other anticancer therapies in participants with HNSCC.

The study consists of a core phase for all cohorts, with a safety run-in and an expansion phase for specific cohorts. The results of an interim analysis after the core phase will decide if the expansion phase will be opened. An overview of the study intervention and disease being treated for each cohort is provided in the table below.

Cohort	Study intervention	Disease
A1	SAR444245 + pembrolizumab	R/M HNSCC treatment-naïve for R/M disease, PD-L1 CPS ≥ 1
A2	SAR444245 + cetuximab + pembrolizumab	R/M HNSCC treatment-naïve for R/M disease, PD-L1 CPS ≥ 1
B1	SAR444245 + pembrolizumab	R/M HNSCC treated with PD1/PD-L1-based regimen & platinum based regimen after failure of no more than 2 regimens for R/M disease
B2	SAR444245 + cetuximab	R/M HNSCC treated with platinum-based regimen & cetuximab-naïve after failure of no more than 2 regimens for R/M disease

CPS: combined positive score; HNSCC: Head and neck squamous cell carcinoma ; PD1: Programmed cell death protein 1; PD-L1: programmed cell death-ligand 1; R/M: Recurrent/metastatic.

Participants who are eligible for both Cohorts A1 (to receive SAR444245 and pembrolizumab) and A2 (to receive SAR444245, pembrolizumab and cetuximab) should be enrolled in Cohort A1 until Cohort A1 enrollment is completed, meaning that cohort A2 will start after cohort A1 completion. For each cohort, SAR444245 will be administered at 24 $\mu\text{g}/\text{kg}$ Q3W. The level might be reduced to [] $\mu\text{g}/\text{kg}$ [] or another lower dose level. Cetuximab will be administered at a dose of 400 mg/m² as an IV infusion on Cycle 1 Day 1 of the study followed by subsequent doses of 250 mg/m² cetuximab IV QW (cohorts A2 and B2). The planned dose of pembrolizumab for this study is 200 mg Q3W (cohorts A1, A2 and B1).

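### The cetuximab dose-reduction rule can never count a reduction made at the second administration, and it cites the SAR444245 dose table

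*SAP*

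**What the plan says.** Section 1.1 sets the planned schedule: "Cetuximab will be administered at a dose of 400 mg/m² as an IV infusion on Cycle 1 Day 1 of the study followed by subsequent" weekly doses of 250 mg/m². Only cohorts A2 and B2 receive cetuximab.

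Section 3.6.1.3 defines a cetuximab dose reduction in three steps:

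- Exemption: "The first and second administration will not be counted as a dose reduction".
- Scope: "For the third and subsequent cetuximab administrations, dose reduction will be determined using the dose level intervals provided in" Table 5.
- Comparator: "If the current dose level is below the dose level interval of the previous dose administration, then the current dose level is considered reduced".

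The cetuximab table below the rule has three levels. The lowest (150 mg/m²) covers ">0 and ≤175 mg/m ²". The middle (200 mg/m²) covers ">175 mg/m ² and ≤225 mg/m ²". The top level is given as "400 mg/m ² then 250 mg/m ²", with the single interval above 225 mg/m². The results feed participant-level counts of any dose reduction and any dose modification.

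Table 5, in section 3.6.1.2, is the SAR444245 table in µg/kg. The cetuximab table is labelled Table 6, a number used again in section 3.6.2 for the ordering of adverse event tables. The SAP's list of tables gives Table 6 only in that second sense and omits the cetuximab table.

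**The concern.** Two features of the rule combine badly. The second administration is exempt, and from the third the reference is the dose actually given the time before, not the dose planned. If the dose is lowered at administration 2, that step is exempt, and the lowered dose then becomes the reference for administration 3. Nothing later in the rule recovers the lost step.

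The exemption was probably meant to stop the planned step from 400 to 250 mg/m² being read as a reduction, although the SAP does not say so. The shared top interval already does this. The exemption is therefore not needed for that purpose, and it removes real reductions at dose 2.

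The SAR444245 rule in section 3.6.1.2 has the same structure but exempts only the first administration. A reduction at the second dose is thus counted for one drug of the regimen and not for the other.

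At stake is the reported share of participants with a cetuximab reduction. Those missed form a specific group: participants whose dose was lowered straight after the loading dose.

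**Working it through.** The SAP gives no figure to reproduce, so the check applies the rule to example sequences.

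**Inputs.** The planned schedule is 400 and then 250 mg/m² weekly (section 1.1). The levels come from the cetuximab table in section 3.6.1.3: level 1 is above 0 and up to 175, level 2 is above 175 and up to 225, and level 3 is above 225 mg/m². The six-dose sequences are illustrative.

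**Rule.** Administration *i* is a reduction if level(dose *i*) < level(dose *i* − 1). As written, *i* starts at 3. The alternative starts at *i* = 2.

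| Sequence (mg/m²) | Levels | Reductions as written | Reductions if assessed from dose 2 |
|---|---|---|---|
| 400/250/250/250/250/250 (planned) | 3,3,3,3,3,3 | 0 | 0 |
| 400/200/200/200/200/200 | 3,2,2,2,2,2 | 0 | 1 (dose 2) |
| 400/150/150/150/150/150 | 3,1,1,1,1,1 | 0 | 1 (dose 2) |
| 400/200/250/250/250/250 | 3,2,3,3,3,3 | 0 | 1 (dose 2) |
| 400/200/200/150/150/150 | 3,2,2,1,1,1 | 1 (dose 4) | 2 (doses 2 and 4) |
| 400/250/200/200/200/200 | 3,3,2,2,2,2 | 1 (dose 3) | 1 (dose 3) |

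- The first row shows that starting at dose 2 raises no false flag on the planned step.
- Rows two to four show participants who had a reduction and are absent from the count as written. This holds whether the reduction was kept or reversed.
- Row five shows that such a participant enters the count only if the dose falls again later.
- Rows two and six differ by one week in the timing of the same reduction. One is counted and the other is not.

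**Size per participant.** The denominator is participants treated. With the approximately 40 per cohort of section 4, 1/40 = 2.5 percentage points.

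**Whether relative dose intensity (RDI) shows the lost step.** For cetuximab, actual and planned dose intensity are divided by the same duration, so RDI = 100 × cumulative dose / sum of planned doses. If the planned dose means the scheduled dose, six doses sum to 400 + 5 × 250 = 1650 mg/m². Then:

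- 200 kept from dose 2: (400 + 5 × 200)/1650 = 1400/1650 = 84.8%.
- 150 kept from dose 2: (400 + 5 × 150)/1650 = 1150/1650 = 69.7%.
- 200 at dose 2 only: (400 + 200 + 4 × 250)/1650 = 1600/1650 = 97.0%.

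**Table reference.** Table 5 is in µg/kg and cannot classify doses in mg/m², so the rule cannot be programmed as cited. The number of the intended table, 6, is shared with another table.

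**The case against.** The logic is hard to dispute. The case on the other side is about weight.

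- **Reach.** Only cohorts A2 and B2 are affected. A participant is lost only if the dose falls at administration 2 and does not fall by a further level later. The document gives no basis for saying how often this happens. This stands: 2.5 points is the weight of one participant, not an estimate of the bias.
- **Any dose modification.** Table 7 groups reduction, omission and delay under modification. On that reading, a participant with another qualifying change still enters this count. This stands: the count is too low only for participants with no other modification.
- **Capture elsewhere.** RDI falls after a sustained reduction, and adverse events leading to dose modification are tabulated separately. This stands in part. RDI depends on what planned dose means, does not show who was reduced or when, and barely moves for a one-dose reduction (97.0% over six doses). The adverse event table covers only changes caused by an event and is not stated to be split by drug.
- **A deliberate convention.** The SAP may have meant to exempt the first administration at each planned level: dose 1 for 400 and dose 2 for 250. That would explain the wording, but the gap remains.
- **Table reference.** The cetuximab table sits directly below the rule, so a programmer would probably find it. This part alone is clerical.
- **The remedy.** Assessing from dose 2 against the previous dose still misses one case. If an interrupted first infusion delivers a dose in the middle interval and dose 2 is 200 mg/m², nothing is flagged. This is correct and is taken up in the fix.

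**Conclusion.** The point holds. As written, a cetuximab reduction at the second administration is never counted, and the participant is missing from the reduction summary unless the dose drops by a further level later. This follows from the rule and the table alone and needs no assumption about the data. The bias in the proportion with at least one reduction can only be downward: 2.5 percentage points per missed participant with 40 treated, and an unknown total. The count of any modification is affected only for participants with no other modification.

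The summaries are descriptive and do not enter any efficacy analysis. The defect should still be corrected, because it gives a wrong count for an identifiable group and treats the two drugs of one regimen differently. The Table 5 citation is also wrong, but that is a minor matter. None of this bears on which cetuximab doses should be given.

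**What to change.** Reword section 3.6.1.3 so that only the first administration is exempt. From the second administration on, each dose would be compared with the level of the previous dose using the cetuximab intervals. This matches the SAR444245 rule and leaves the planned 400-to-250 mg/m² step unflagged.

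A somewhat stronger option is to compare each dose from the second on with the interval of the dose planned in the schedule for that administration. This also covers an incomplete first infusion. If it is chosen, the SAP should say that the count is of doses below plan rather than of steps down.

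In either case:

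- replace the Table 5 reference with the cetuximab table;
- give that table a unique number, add it to the list of tables, and update later table numbers and cross-references;
- state that planned dose in the cetuximab planned dose intensity means the scheduled dose, if that is the intention, so that RDI reflects a sustained reduction.

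The cost is SAP wording and one changed line in the derivation specification. No new data are needed.

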3.6.2 Adverse events

General common rules for adverse events

All AEs will be graded according to National cancer institute common terminology for adverse events (NCI-CTCAE version 5.0) and coded to a lower-level term (LLT), preferred term (PT), high-level term (HLT), high-level group term (HLGT), and associated primary system organ class (SOC) using the Medical Dictionary for Regulatory Activities (MedDRA) version currently in effect at Sanofi at the time of database lock. Cytokine Release Syndrome (CRS) and Immune effector cell associated neurotoxicity syndrome (ICANS) will be graded using ASTCT Consensus grading.

The AEs will be analyzed in the following 3 categories:

- Pre-treatment AEs: AEs occurring during the pre-treatment period.
- Treatment-emergent adverse events (TEAEs): AEs that developed, worsened (according to the Investigator's opinion) or became serious during the treatment-emergent period
- Post-treatment AEs: AEs that developed, worsened, or became serious during the post-treatment period.

Similarly, the deaths will be analyzed in the pre-treatment, treatment-emergent and post-treatment periods.

The primary AE analyses will be on TEAEs. Pre-treatment and post-treatment AEs will be described separately.

An AE with incomplete or missing date/time of onset (occurrence, worsening, or becoming serious) will be classified as a TEAE unless there is definitive information to determine it is a pre-treatment or a post-treatment AE.

If the assessment of the relationship to IMP is missing for an AE, this AE will be assumed as related to IMP. Missing grade will be left as missing.

Multiple occurrences of the same event in the same participant will be counted only once in the tables within a treatment phase, using the maximum (worst) grade by treatment phase. Summaries will be provided for all grades combined and for Grade ≥ 3 (including Grade 5). Missing grades, if any, will be included in the "all grades" category.

The AE tables will be sorted as indicated in [Table 6](#).

Table 6 - Sorting of AE tables

AE presentation	Sorting rules
SOC, HLG, HLT and PT	By the internationally agreed SOC order and by alphabetic order of HLGs, HLTs and PTs.
SOC and PT	By the internationally agreed SOC order and decreasing frequency of PTs ^{a,b}
PT	By decreasing frequency of PTs ^a

^a Sorting will be based on the AE incidence.

^b The table of all TEAEs presented by primary SOC and PT will define the presentation order for all other tables (eg, treatment-emergent SAE) presented by SOC and PT, unless otherwise specified.

Analysis of all adverse events

The overview of TEAE with the details below will be generated:

- Any TEAE
- Any Grade ≥ 3 TEAE
- Any treatment-emergent SAE
- Treatment related TEAEs
- Treatment related TEAE of Grade ≥ 3
- Serious treatment related TEAEs
- Grade 5 TEAE (any TEAE with a fatal outcome during the treatment-emergent period)
- Any TEAE leading to permanent full intervention discontinuation
- Any TEAE leading to permanent partial intervention discontinuation (discontinuation of each individual drug)

The AE summaries of [Table 7](#) will be generated with number (%) of participants experiencing at least one event. The analyses will be performed for all grades combined and for grades ≥ 3 . The all TEAE summary by Primary SOC and PT (and other safety summaries (eg, SAEs, deaths), if deemed needed after TEAE evaluation) will be performed by trial impact (disruption) due to COVID-19.

Table 7 - Analyses of adverse events

Type of AE	MedDRA levels
All TEAE	Primary SOC, HLTG, HLT and PT Primary SOC and PT
TEAE related to IMP (overall) as per Investigator's judgment	Primary SOC and PT
Treatment emergent SAE	Primary SOC and PT
Treatment emergent SAE related to IMP (overall) as per Investigator's judgment	Primary SOC and PT
TEAE leading to permanent full intervention discontinuation	Primary SOC and PT
TEAE leading to permanent partial intervention discontinuation (for each individual drug)	Primary SOC and PT
TEAE leading to death (death as an outcome of the AE as reported by the Investigator in the AE page)	Primary SOC and PT
AE leading to death ^a	Primary SOC and PT
- In context of disease progression ^b	
- In context other than disease progression ^c	
Pre-treatment AE	Primary SOC and PT
Post-treatment AE	Primary SOC and PT
TEAE leading to dose interruption	Primary SOC and PT
TEAE leading to dose modification (including dose reduction, dose omission and dose delay)	Primary SOC and PT

a Death as an outcome of the AE as reported by the Investigator in the AE page

b Death within 30 days from last IMP administration and the cause of death is disease progression

c Death within 30 days from last IMP administration and for whom cause of death is not disease progression or the death occurred more than 30 days from last IMP administration and the cause of death is AE

Analysis of deaths

In addition to the analyses of deaths included in [Table 6](#), the number (%) of participants in the following categories will be provided:

- Deaths during the treatment-emergent and post-treatment periods by main reason for death
- An overview of Grade 5 AEs will be provided with the following categories:
 - Grade 5 AE (TEAE and post-treatment).
 - Fatal TEAE (regardless of date of death/period).
 - Grade 5 TEAE with a fatal outcome during the treatment-emergent period,
 - Any Grade TEAE with a fatal outcome during the post-treatment period.
 - Post-treatment Grade 5 AE (excluding a TEAE that worsened to Grade 5 during the post-treatment period).

Analysis of adverse events of special interest (AESIs)

Number (%) of participants experiencing at least one adverse event of special interest will be provided, by system organ class (SOC) and preferred term (PT). The selection will be made using the electronic case report form (eCRF) specific AESI tick box. Tables will be sorted as indicated in [Table 6](#).

In addition, the following analyses will be done for infusion reactions categories (ie, infusion related reactions [IRRs], cytokine release syndrome [CRS], flu-like symptoms [FLS] and anaphylaxis):

- Description of the infusion reactions by predefined grouping and other reported PT
- Worst grade
- Action taken for each IMP
- Corrective treatment given (Yes, No)
- Number (%) of patients with only 1 episode, ≥ 2 , ≥ 3 , ≥ 4 and ≥ 5 episodes
- Onset of first episodes of infusion reactions (at the first infusion and subsequent infusions)
- Number (%) of patients with infusion reactions (any episodes) at the first and subsequent infusions
- Number (%) of patients with at least one infusion with two episodes of infusion reactions
- Total number of infusion reaction episodes
- Time to onset from infusion (by category: infusion day/1 day after infusion/2 to 3 days from infusion/More than 3 days from infusion when applicable)
- Duration of infusion reactions (in days) (by category 1 day/2 to 3 days/more than 3 days/not recovered)
- Number (%) of patients with infusion reactions symptoms (as reported by Investigator) by SOC and PT.

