3 STATISTICAL ANALYSES

3.1 GENERAL CONSIDERATIONS

In general, continuous data will be summarized using the number of observations available, mean, standard deviation (SD), median, minimum, and maximum. Categorical and ordinal data will be summarized using the count and percentage of participants.

The baseline value is defined as the last available value before the first administration of any of the three IMPs (SAR444245 or cetuximab or pembrolizumab). For participants enrolled but not treated, the baseline value is defined as the last available value before enrollment.

Unless otherwise specified, analyses will be performed by cohort, by dose and overall (if applicable). Participants enrolled in the safety run-in part and treated at the RP2D will be included in the analyses of the core phase.

All efficacy analyses will be performed on the efficacy population. Objective Response Rate (ORR), as well as all other response-related efficacy endpoints will be primarily derived using the Investigator's assessment for all cohorts and using Response Evaluation Criteria in Solid Tumor (RECIST 1.1).

Central imaging may be done retrospectively if significant activity is observed (See [Section 3.2.3](#) for sensitivity analysis).

Confidence intervals will be two-sided 90% CI for efficacy analyses and will be used for descriptive purposes only, without inference.

The BOR is defined as the best overall response observed from the date of first investigational medicinal product (IMP) until disease progression, death, cut-off date or initiation of further anti-cancer therapy, whichever occurs first. Also:

- A PR or a CR must be confirmed on a second imaging done at least 4 weeks apart, in order to confirm the antitumoral response.
- A SD response must be assessed at least 6 weeks after the first IMP administration to be considered as evaluable.

All safety analyses will be performed on the exposed population.

Analysis period

The analysis period will be divided into 3 segments:

- The **pre-treatment period** is defined as the time from when the participants give informed consent to the first administration of the IMP.
- The **on-treatment period** (ie, treatment-emergent [TE] period) is defined as the time from the first administration of IMP up to 30 days after the last administration of IMP.

- The **post-treatment period** is defined as the time from the end of the on-treatment period, ie, 31 days after the last administration of IMP.

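### SAP Table 7 places some fatal AEs with death more than 30 days after last IMP in neither progression sub-row, so the sub-rows need not sum to their parent row

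*SAP*

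**What the plan says.** Everything relevant is in SAP Section 3.6.2, apart from the definition of the analysis periods in Section 3.1.

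- **Parent row of Table 7 (AE leading to death).** Footnote a uses the same criterion as the TEAE row above it: "death as an outcome of the AE as reported by the Investigator in the AE page". It sets no limit on the time since last dose.
- **Sub-row for the progression context (footnote b).** "Death within 30 days from last IMP administration and the cause of death is disease progression".
- **Sub-row for the context other than progression (footnote c).** There are two limbs joined by 'or': "Death within 30 days from last IMP administration and for whom cause of death is not disease progression", and "the death occurred more than 30 days from last IMP administration and the cause of death is AE".
- **The 30-day limit.** It matches the end of the on-treatment period in Section 3.1, which is "the time from the first administration of IMP up to 30 days after the last administration of IMP".
- **Related summaries under the analysis of deaths.** One is "Deaths during the treatment-emergent and post-treatment periods by main reason for death". The overview of Grade 5 AEs includes "Fatal TEAE (regardless of date of death/period") and a line for TEAEs that become fatal in the post-treatment period.

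**The concern.** The labels of the two sub-rows read as complements: in the context of progression, and in any other context. A reader of the clinical study report will expect the two counts to add up to the row above them. They need not, because the time limit is applied unevenly. After 30 days the progression sub-row is closed, while the other sub-row stays open for deaths caused by an AE. A participant with a fatal AE who dies on day 45 after last IMP with progression as the recorded cause is counted as having an AE leading to death, but appears in neither context.

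The study is uncontrolled, so no comparator shows how many fatal AEs the underlying cancer would produce. Among the summaries listed in Section 3.6.2, these sub-rows are the only ones that divide fatal AEs by progression context. If they are incomplete without saying so, the table gives a partial answer to the question it was built for.

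**Working it through.** The SAP gives no figure to reproduce here, so the check is one of logic.

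**Inputs.** Footnotes a, b and c of Table 7 as quoted above. Time of death is either at most 30 days or more than 30 days after last IMP. Cause of death is progression, AE, or other/unknown. All participants considered have a fatal AE on the AE page, so all are in the parent row.

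**Assignment of the 2 × 3 = 6 cells.**

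| Time of death | Cause of death | Parent row | Progression (b) | Other than progression (c) |
|---|---|---|---|---|
| ≤ 30 days | Progression | yes | yes | no |
| ≤ 30 days | AE | yes | no | yes (first limb) |
| ≤ 30 days | Other/unknown | yes | no | yes (first limb) |
| > 30 days | Progression | yes | **no** | **no** |
| > 30 days | AE | yes | no | yes (second limb) |
| > 30 days | Other/unknown | yes | **no** | **no** |

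Four cells are assigned once, none twice, and 6 − 4 = 2 not at all. Hence parent = b + c + (late progression) + (late other/unknown). The sub-rows sum to the parent only when both late cells are empty.

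**Can the omitted cells be occupied?** The SAP provides for fatal AEs with late death, because its Grade 5 overview has a line for TEAEs with a fatal outcome in the post-treatment period. It also treats the AE-page outcome and the cause of death as separate criteria: footnote b exists for the combination of a fatal AE and progression as the cause. How many such participants there will be cannot be told from the SAP.

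**Direction of any distortion.** Take two hypothetical sets of 10 participants with a fatal AE. In both, 6 die within 30 days (3 of progression, 3 not) and 4 die later.

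- *Set 1: late deaths are 2 progression, 2 AE.* Table 7 shows b = 3 and c = 3 + 2 = 5, so c is 5/8 = 62.5% of those classified. Classified by cause alone, the split is 3 + 2 = 5 and 3 + 2 = 5, so the share is 5/10 = 50%. The table overstates the share other than progression.
- *Set 2: late deaths are 0 progression, 2 AE, 2 other.* Table 7 again shows b = 3 and c = 5 (62.5% of 8). Classified by cause alone, the split is 3 and 3 + 2 + 2 = 7, so the share is 7/10 = 70%. The table understates it.

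Both sets give the same two sub-row counts, and each leaves 10 − 8 = 2 participants unclassified. The size of the omission is visible from the parent row. Its direction is not.

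**The case against.** The best defence is that the pattern is intended. Thirty days is the treatment-emergent window. Inside it, every fatal AE is assigned a context. Beyond it, only deaths attributed to an AE are of interest, and footnote c keeps all of those in view. On this reading, late progression deaths belong in the tables of deaths. No AE-caused death is hidden, every affected participant stays in the parent row, and late deaths also appear in the summary by main reason and, for TEAEs, in the Grade 5 overview. Table 7 does not claim that its sub-rows are exhaustive, and it plans no percentage of one sub-row among those classified. The shares in the worked example are therefore illustrative and are not planned outputs.

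Much of this stands, and it limits the consequence. It does not close the gap. The SAP states no such rationale and carries no note that the sub-rows are incomplete. The summary of deaths by reason covers all deaths, not only participants with a fatal AE, and the Grade 5 overview has no division by progression. What is lost is the cross-classification of fatal AEs by a late cause of death other than AE.

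A reader might go further and infer that the table always inflates the fatal AEs not explained by the cancer, and more so at the final cut-off (3 years from cohort last patient in) than at the primary one (about 9 months from the last participant's first infusion). The document does not support that. Footnote c also stops at 30 days for every cause except AE, so late deaths are lost from both contexts and the two losses pull in opposite directions, as sets 1 and 2 show. Whether the omission grows with follow-up depends on how long AEs are collected after last dose, which the SAP does not settle.

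**Conclusion.** The point holds as one about completeness. Footnotes b and c leave two of six time-by-cause cells unassigned, both after 30 days: progression, and causes that are neither progression nor AE. Read by its label, the progression sub-row is undercounted whenever a participant with a fatal AE dies of progression after 30 days, and the sub-rows need not sum to the parent row. This follows from the wording alone and needs no assumption about event rates.

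A general upward bias in the row other than progression is not established, nor is growth of any bias with a later cut-off. The practical impact is modest. The table is descriptive, the affected participants remain in the parent row, and neither the primary endpoint nor any decision rule in the SAP uses the split. It merits correction because the gap is certain, the table concerns fatal events in an uncontrolled study, and the change is small.

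**What to change.** Either of two edits makes the sub-rows sum to the parent row.

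1. **Same time for both contexts.** Define footnote b as cause of death is disease progression, and footnote c as cause of death is anything else, including unknown. Show each separately for deaths up to 30 days and more than 30 days after last IMP, which gives four cells that add up to the parent row.
2. **Keep b and c and add a row.** Insert a third sub-row for deaths more than 30 days after last IMP with a cause other than AE (progression, other or unknown). This keeps the present definitions if the 30-day limit on progression deaths is intended.

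The first is clearer, because it shows late progression deaths with fatal AEs as a count of their own. The cost is a change to two footnotes, or one added row, and the matching table shell. The existing footnotes already require date and cause of death, so no new data are needed.
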